7.1.1.4 Relationship to Intervention Assessment

Relationship of NCG to the adverse event or suspected adverse reaction is defined as follows:

- **Unrelated:**
Adverse event is clearly due to extraneous causes (e.g., underlying disease)
- **Unlikely related (must have 2 of the below):**
Does not have temporal relationship to NCG administration
Could readily have occurred due to subject's clinical state
Could have been due to environment or other interventions
Does not follow known pattern of response to NCG
Does not reappear or worsen with reintroduction of NCG
- **Possibly related (must have 2 of below):**
NCG administration and the occurrence of the AE are reasonably related in time
Could not readily have occurred due to subject's clinical state
Could not readily be due to environment or other interventions
Follows a known pattern of response to NCG
- **Probably related (must have 3 of the below):**
NCG administration and the occurrence of the AE are reasonably related in time
Could not readily have occurred due to subject's clinical state
Could not readily be due to environment or other interventions
Follows a known pattern of response to NCG
- **Definitely related (must have all 4 of the below):**
NCG administration and the occurrence of the AE are reasonably related in time
Could not readily have occurred due to subject's clinical state
Could not readily be due to environment or other interventions
Follows a known pattern of response to NCG

7.1.2 Collection and Reporting of Adverse Events

The site study coordinator is responsible for collecting and recording all clinical and laboratory data. Adverse events will be collected on subjects on each day of admission, as well as by phone or e-mail communication with parents when the study coordinator contacts subjects or their families to collect any adverse events that occurred in the 72 hours following episode treatment completion following each admission. The reporting period for new AEs is the period from the start of study drug administration until the patient completes their participation in the study (i.e., until the end of the study period or until discontinuation if early withdrawal occurs). Follow-up reports on AEs should continue up to 30 days after the administration of study treatment if the AE did not resolve.

For each AE, the site investigator will assess severity, and whether the event meets the definition of a serious adverse event (see Section 7.1.1) and will report whether study treatment was interrupted or stopped, as well as the outcome of the AE. If the event is an SAE, both the site PI and the Medical Monitor will assess the relationship to study treatment. As described in 5.7.3, treatment assignment should not be unblinded unless the Medical Monitor assesses that knowledge of drug assignment is required in order to assess how to treat a safety concern within a patient.

[figure not shown]
If a non-serious adverse event is unresolved at the time of discharge from the study, the site PI will make a clinical assessment as to whether continued follow-up of the AE is warranted. The

site PI may request input from the Medical Monitor. Resolution is defined as the return to baseline status or stabilization of the condition with the expectation that it will remain chronic.

The CNMC-CC will prepare aggregate reports of all adverse events (serious/not serious and expected, unexpected) for the DSMB as required and for the FDA on an annual basis. Local site investigators are also required to fulfill all reporting requirements to their IRB and to the CNMC-CC.

7.1.2.1 Reporting of Serious Adverse Events

Serious adverse events (SAEs) must be reported by each site PI to the CNMC-CC within 24 hours of learning of the event. The CNMC-CC has a joint phone & email tree for reporting SAEs to the CNMC-CC at any time. Those involved in the phone & email tree are aware that they may expect to receive a phone call or email at any time for an SAE. The site reporting the SAE must attempt to call or email first the CNMC-CC Principal Investigator (PI), followed by the Project Manager (PM), and then the Data Manager (DM) until someone has been reached in real time. It will be the responsibility of the CNMC-CC PI, PM, and DM to have a backup point of contact for instances of sick leave or vacation.

The Medical Monitor (or their delegate) will then be contacted by the CNMC-CC and be informed of the details of the SAE. The CNMC-CC will immediately report unexpected SAEs to the CNMC IRB according to local guidelines.

Sites are required to submit follow-up reports to the initial report as promptly as is feasible. The CNMC-CC will submit a report of the SAE to the FDA within 15 calendar days of the event if the event meets the reporting requirement of a serious and unexpected suspected

adverse reaction (SUSAR). In those cases, the CNMC-CC will also report the event to the DSMB. In all other cases, the CNMC-CC will submit the report as part of periodic reporting to the DSMB and FDA.

The Medical Monitor will review causality (unrelated, not likely related, possibly related, probably related, definitely related) of the serious adverse event. The Medical Monitor may request further information if necessary and possibly request changes to the protocol or consent form as a consequence of the adverse event.

Additionally, site investigators will be responsible for reporting SAEs to their IRB within the time mandated by the site IRB. The CNMC-CC will inform all sites of any safety updates or changes, and the site investigators will be responsible for notifying their local IRB of these modifications. The CNMC-CC will ensure that all SAEs and any safety updates or changes are reported to the site's IRB by collecting a copy of all IRB-related correspondence and reviewing regulatory submissions during monitoring visits.

7.2 Data and Safety Monitoring Board (DSMB)

A DSMB will be assembled by the investigators. Typically, the Board members represent the following specialties, all of whom will have no formal involvement with the participants or the investigators: a medical doctor with experience in inherited metabolic disorders, a neonatologist, a biostatistician, and the clinical trial coordinator. This Board is responsible for safety and accuracy monitoring of the data entered by the investigators. The DSMB will regularly evaluate trial performance, monitor interim data for safety and effectiveness of study regimens, review any protocol modifications, and advise the investigators regarding early termination or continuation of a study based on the interim monitoring or scientific findings. The DSMB will receive and respond to reports of any serious adverse events (SAEs) and will be immediately notified of fatal or life-threatening events. Based on the review of safety, efficacy, and performance data, the DSMB will make recommendations regarding the conduct of the study. It is expected that the DSMB will meet at least biannually in Washington, D.C., with conference calls as necessary.

7.3 Medical Monitor

A Medical Monitor has been identified by the investigators. The Medical Monitor is responsible for being available by pager to monitor study safety issues and must identify an appropriate delegate to provide coverage whenever he is not available. The Medical Monitor (or designee) will be contacted whenever a critical situation with a patient arises and a decision about unblinding the treatment assignment must be made (i.e., in the event that unblinding the treatment assignment would affect subsequent management of the patient). The Medical Monitor may be unblinded whenever he deems it necessary. The Medical Monitor will also conduct an independent blinded review of all Serious Adverse Events (SAEs) and will contribute to the preparation of all SAE reports. The Medical Monitor will communicate any identified safety concerns to the study PI and Coordinating Center. The Medical Monitor may consult with the DSMB.

8 STATISTICAL ANALYSIS

8.1 Study Aims

8.1.1 Primary Aim

The primary aim is to evaluate the impact of NCG treatment during hyperammonemic events on the resolution of ammonia levels, among patients diagnosed with severe PA or MMA and partial CPSD or OTCD.

8.1.2 Secondary Aim

Secondary analyses will also evaluate the safety of NCG. Safety is a secondary aim because there is already evidence that NCG, which is approved by the FDA for use in the treatment of NAGS, poses no serious risks to patient safety. Therefore, the focus of this research is less on safety than on its effectiveness in treating PA and MMA, which share the common risks associated with hyperammonemia with NAGS. The analysis of safety will focus on three outcomes; these include the level of selected laboratory markers related especially to organ health, the frequency of reported symptoms, and the frequency of reported adverse events by seriousness. The analysis of laboratory markers will compare the time specific and time averaged mean levels of each marker by study group. In addition, we will compare the frequency of symptoms and adverse events, relying mainly on tabulations by a study group of reports by organ system paying most attention to the magnitude of the difference between groups and consistency of the evidence than on formal hypothesis testing.

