| | 
methylmalonic acid levels and no evidence of biotin-related disorders in the organic acid analysis OR
 
 ▪ Diagnosed with MMA by semi-quantitative urine organic acid analysis, defined as elevation of methylmalonic acid and no evidence of vitamin B12 dependent disorder on plasma amino acid analysis (B12 dependency is defined by documented B12 responsiveness) ▪ AND: Subject or subject's first-degree relative had plasma ammonia level at any time ≥ 100 mcmol/L 
 ○ Able to receive medications orally, by nasogastric (NG)-tube or by Gastric (G)-tube ○ No concomitant illness which would preclude safe participation as judged by the investigator ○ If post-menarcheal must have a negative pregnancy test prior to administration of study drug at each episode ○ Signed informed consent by the subject or the subject's legally acceptable representative 
Exclusion criteria
 
 ○ Administration of NCG within 7 days of participation in the study ○ Use of any other investigational drug, biologic, or therapy ○ Planned participation in any other clinical trial ○ Diagnosis of any medical condition causing hyperammonemia which is not PA, MMA, CPSD, OTCD ○ Any clinical or laboratory abnormality or medical condition that, at the discretion of the investigator, may put the subject at an additional risk by participating in this study ○ Had a liver transplant ○ Is pregnant ○ Is not expected to be compliant with the study 
Patients enrolled in the now-closed long-term outcomes study being conducted in parallel are eligible to enroll in this study provided that all other inclusion and exclusion criteria are satisfied.
 |
| Primary Outcome Measures: | Composite of the shortest of the time to reach an ammonia level <50 mcmol/L or time to discharge from the hospital after the first dose of NCG. Safety of NCG treatment as measured by serious adverse events, electrocardiogram test and laboratory blood tests |

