2.2 Safety

[figure not shown]
The primary safety outcome of the study will be the rate of Serious Adverse Events (SAEs) during study episodes defined in this study as death or substantial prolongation of hospitalization, as patients are hospitalized as part of having a qualifying hyperammonemia episode. Safety tests consisting of complete blood count (CBC), liver and kidney function tests, coagulation profile (PTT/INR) will be performed before treatment, on the third day of treatment, just prior to episode treatment completion of NCG and thirty days (up to six months) after the last study dose. Patients in a hyperammonemia crisis frequently experience transient anemia once appropriately hydrated during an emergency room visit. In order to monitor the transient anemia, in addition to collecting CBC's, if a patient receives a blood transfusion during hospitalization this information will also be collected. An EKG test will be performed before treatment and between days 3-5 of treatment or before discharge if earlier.

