- **Electrocardiogram (EKG) Test** – At each episode, participants will have an EKG at admission and repeated on day 3-5 of treatment (48 hours following the initial drug administration, before discharge if earlier) to check for cardiac toxicity.
- **Functional Scale Score (FSS)** – Determined for each episode at admission and every day of hospitalization for a total of 7 days or until discharge, whichever is shorter.
- **Recurrent Episodes** – Each subsequent admission for metabolic decompensation will follow the same above procedure but has to occur at least 7 days after the last discharge to guarantee study drug wash out before the next administration should patient have received study drug.

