5.5.2 Electrocardiogram test (EKG)

QT interval and QTc interval will be collected from each EKG, along with any abnormalities noted in the interpretation

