Secondary efficacy outcomes are based on groupwise comparisons of the trajectory (slope) of ammonia decline, FSS, and time-to-hospital-discharge during hyperammonemia episodes. For analysis of the ammonia decline trajectory and FSS analysis, we will implement longitudinal linear hierarchical models. The models will enable us to estimate and compare the slope(s) based on ammonia change trajectory over time, as well as the time, averaged FSS across all episodes treated with NCG vs. PLBO. For time to discharge comparisons, we will rely on the same Cox Regression Analysis described for the primary outcome except the outcome event will be limited to time to discharge. As in the primary analysis, we will adjust model error for the clustering of observations by patient and control for severity based on ammonia level or FSS at admission to each episode. To assess NCG safety we will compare the levels/frequency of laboratory test results, reported symptoms, and adverse events. Secondary analyses will control for indicators of episode severity, e.g. peak ammonia.

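### EKG is a listed safety measure with paired QTc readings, but the stated safety analysis gives it no comparison, and laboratory markers are compared without their pre-dose values

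*Combined protocol and SAP*

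**What the plan says.** **What is measured.** Under Primary Outcome Measures the synopsis gives "Safety of NCG treatment as measured by serious adverse events, electrocardiogram test and laboratory blood tests". Section 3.1 requires an EKG at admission of each episode, "repeated on day 3-5 of treatment (48 hours following the initial drug administration, before discharge if earlier) to check for cardiac toxicity". Section 5.5.2 adds that "QT interval and QTc interval will be collected from each EKG", together with abnormalities noted in the interpretation. Section 5.5.6 lists EKG tests, with serious and other adverse events and safety laboratory values, as assessments of NCG against placebo. For transient anemia, section 2.2 says that "if a patient receives a blood transfusion during hospitalization this information will also be collected"; Table 1 has a transfusion log, and section 5.5.3 records type and units.

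**What is analysed.** Section 8.1.2: "The analysis of safety will focus on three outcomes; these include the level of selected laboratory markers related especially to organ health". The second and third outcomes are the frequency of reported symptoms and the frequency of adverse events by seriousness. Laboratory markers are to be compared by group on time-specific and time-averaged means. Section 8.3 repeats the list: "To assess NCG safety we will compare the levels/frequency of laboratory test results, reported symptoms, and adverse events". It adds that secondary analyses control for episode severity, with peak ammonia as the example.

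**Rank of the safety measures.** Section 2.2 states: "The primary safety outcome of the study will be the rate of Serious Adverse Events (SAEs) during study episodes". Section 8.1.2 calls safety a secondary aim.

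**The concern.** A measure taken at every episode for a stated toxicity purpose should have a stated analysis. Without one, the QTc summary would be chosen after the data are seen: mean or maximum, change or on-treatment value, adjusted or not. The DSMB, which under section 8.3.1 weighs safety at the interim look, would have no defined EKG content. Adverse event reporting is a weak substitute. A shift in mean QTc without symptoms need not be reported as an event, and section 7.1.1.3 lists cardiomyopathy among the complications of PA, so cardiac events may be put down to the disease. The randomised comparison of paired readings is what separates drug from disease.

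The laboratory comparison has a related weakness. These patients are acutely ill at entry, their starting values can be expected to vary, and a pre-dose value is drawn at each episode, but the stated method does not use it.

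**Working it through.** **1. Measures set against analyses.** The plan states no figure on this point, so the check is of text.

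| Measure | Named as outcome or assessment | How collected | Analysis in 8.1.2 and 8.3 |
|---|---|---|---|
| Adverse events, including serious | Synopsis (serious), 2.2 (serious), 5.5.6 | Adverse event log, 7.1.2 | Frequency by group and seriousness |
| Laboratory tests | Synopsis, 2.2, 5.5.6 | 5.4.1.2, Table 1, 5.5.1 | Time-specific and time-averaged means by group |
| EKG | Synopsis, 2.2, 3.1, 5.5.6 | 5.4.1.2, Table 1, 5.5.2 | None |
| Transfusions | 2.2 | Table 1 log, 5.5.3 | None |
| Reported symptoms | Only 8.1.2 and 8.3 | No separate log or checklist; may enter as adverse events | Frequency by group |

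No section gives a QTc endpoint, a change from baseline, an abnormality category, a model or a table for EKG.

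**2. Precision available for QTc (illustration).** The target is 114 episodes (section 8.4), so 114 / 2 = 57 per arm. The documents give no QTc variability. Assumptions: SD 20-30 ms, correlation r = 0.6 between pre-dose and on-treatment QTc, a complete EKG pair at every episode, and clustering by patient ignored.

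Half-width of the 95% CI = 1.96 x SD x sqrt(2/57) x sqrt(1 - r^2), with sqrt(2/57) = 0.187 and sqrt(1 - 0.36) = 0.8.

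- SD 25, unadjusted (factor 0.8 omitted): 1.96 x 25 x 0.187 = 9.2 ms
- SD 25, adjusted: 9.2 x 0.8 = 7.3 ms
- SD 20, adjusted: 1.96 x 20 x 0.187 x 0.8 = 5.9 ms
- SD 30, adjusted: 1.96 x 30 x 0.187 x 0.8 = 8.8 ms

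At r = 0.6, using the pre-dose reading narrows the interval by one fifth (1 - 0.8). The same factor applies to any laboratory marker with that correlation.

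**3. Laboratory time average.** If a constant on-treatment shift d is averaged over m draws, of which k are on treatment, the expected difference is d x k/m.

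- One pre-dose and two on-treatment draws (the section 3.1 schedule for a full stay): 2/3 of d, a loss of one third.
- Early discharge with one on-treatment draw: 1/2 of d.
- If the post-treatment draw in section 2.2 (thirty days, up to six months) is also averaged and the effect has gone by then: 2/4 = 1/2 of d.

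Which case applies, if any, depends on which draws enter the average. Section 8.1.2 does not say.

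**The case against.** The strongest reply is section 5.5.6, which sets EKG out by treatment group. The comparison is therefore named and only its method is missing. Section 8.1.2 says that the analysis will focus on three outcomes, which is not an exclusion, and EKG abnormalities can be reported as adverse events, tabulated by organ system. This stands in part. A reader might infer that the cardiac question must go unanswered, and the documents do not support that. But section 5.5.6 gives no summary or model, and both sections that define the safety analysis leave EKG out.

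Other points have weight:

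- A reader might take EKG to be a primary safety endpoint that was dropped. That status rests on the synopsis alone; section 2.2 makes the serious adverse event rate primary and section 8.1.2 makes safety secondary.
- A reader might infer that no form collects symptoms. This cannot be shown. The case report forms are not in the documents (section 10.8 says that they will be developed), the adverse event definition in section 7.1.1.1 is broad, and section 7.1.1.3 lists vomiting and lethargy as expected events.
- Transfusion records are not without use. They serve the monitoring purpose in section 2.2; what is missing is a comparison by arm.
- The time-specific laboratory comparisons on treatment are not diluted by the pre-dose draw, and because episodes are randomised, leaving out baseline costs precision, not validity. This is right. The control for severity in section 8.3, however, does not replace adjustment for a marker's own starting value.
- Section 1.3.1 reports no QT or QTc change in dogs, and a simple table by arm might be thought enough for a Phase II trial. That bears on how elaborate the analysis should be. The protocol still chose to check cardiac toxicity in these patients.

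**Conclusion.** The plan should be changed. EKG is listed, timed, recorded and named as a comparison between arms, but it has no prespecified analysis; transfusions have no comparison by arm; and reported symptoms have no specified instrument apart from the adverse event log. These conclusions rest on the text alone.

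The laboratory point is an improvement rather than an error of validity. The loss of precision depends on the correlation with the pre-dose value. The one-third dilution applies only if the pre-dose draw enters the time average and there are two on-treatment draws.

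The QTc half-width of 5.9-8.8 ms is illustrative. It rests on an assumed SD and correlation, complete pairs and no clustering. The second EKG may also fall anywhere from before an early discharge to days 6-7 (section 5.4.1.3), so exposure at that reading will differ. A reader might infer that the trial could rule out a mean shift of 10 ms. That is too strong: with no true shift, the chance that the upper 95% limit falls below 10 ms is about 76% at SD 25 adjusted, 60% at SD 30 adjusted, and 57% at SD 25 unadjusted.

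**What to change.** In sections 8.1.2 and 8.3:

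1. Add EKG as a safety outcome: on-treatment QTc by arm, adjusted for the same episode's pre-dose QTc and allowing for repeat episodes per participant, with counts of new EKG abnormalities by arm. State how many episodes have a complete pair.
2. Tabulate transfusions by arm.
3. Compare on-treatment laboratory values adjusted for the same episode's pre-dose value, and exclude the pre-dose draw from the time average. State whether the late post-treatment draw is included.
4. Fold reported symptoms into adverse events, or state how they are collected. Do not simply delete them.
5. Reconcile the synopsis with sections 2.2 and 8.1.2 on whether EKG is a primary safety measure.
6. Put the same tables in the DSMB reports.

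The cost is analysis wording and a few extra tables. The data are already collected, with no added visits or tests.

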5.4.1.2 Concurrent with Randomization

Pre-Treatment

1. Indicated clinically, a blood sample will be drawn for plasma ammonia and amino acid analysis. All patients are expected to have clinically indicated vascular access. If vascular access is inadequate, blood will be drawn by venipuncture. All ammonia levels measured up to 24 hours prior to first treatment administration will be recorded. Ammonia levels measured >24 hours prior to first treatment administration will not be recorded in this study.
2. Laboratory safety assessments: complete blood count (CBC), liver function tests (LFT), renal function test (RFT), amylase and lipase. If indicated clinically, a coagulation profile (PTT and INR) should also be done. A pregnancy test is required (if applicable).
3. Electrocardiogram (EKG) test
4. Functional Status Scale (FSS) assessment

Table 1. Hospitalization Study Procedures

Short-Term Outcome of NCG in Hyperammonemia

| | Day 1 | | | | | Day 2 | | Day 3 | | Day 4 | | Day 5 | | Day 6 | | Day 7 | | Day 30 (≤6 Months) |
|--|-------|---------------|---|----|----------------|-------|----|-------|----|----------------|----|----------------|-----|----------------|-----|----------------|-----|-----------------------|
| Time (hours) | 0 | Post Dialysis | 6 | 12 | 18 | 24 | 36 | 48 | 60 | 72 | 84 | 96 | 108 | 120 | 132 | 144 | 156 | |
| Confirm Eligibility | X | | | | | | | | | | | | | | | | | |
| Pregnancy Test^b | X | | | | | | | | | | | | | | | | | |
| Randomization | X | | | | | | | | | | | | | | | | | |
| Plasma Ammonia Level^c | X | (X) | X | X | X ^d | X | X | X | | X ^f | | X ^f | | X ^f | | X ^f | | |
| Plasma Amino Acids^c | X | (X) | | | | X | | | | X ^g | | | | X ^g | | | | |
| Safety Labs^c | X | | | | | | | | | X ^h | | | | X | | | | |
| EKG Testⁱ | X | | | | | | | | | X ⁱ | | | | | | | | |
| Functional Status Scale^c | X | | | | | X | | X | | X | | X | | X | | X | | X |
| Concomitant Medications Log | | | | | | X | | X | | X | | X | | X | | X | | X |
| Adverse Events Log | | | | | | X | | X | | X | | X | | X | | X | | X |
| Study Drug (NCG or PLBO) | X | | | | X | X | X | X | X | X | X | X | X | X | X | X | X | |
| Treatment Administration Log | X | | | | X | X | X | X | X | X | X | X | X | X | X | X | X | |
| Blood Transfusion Log | X | | | | X | X | X | X | X | X | X | X | X | X | X | X | X | |

NCG=N-carbamylglutamate; PLBO=Placebo

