^a Suggested timeline to be followed for 7 days, or until discharge if discharged prior to 7 days of drug administration

^b For women of childbearing potential only. A serum pregnancy test will be performed in the event of a positive or equivocal urine pregnancy test result, or if the patient is anuric

^c Allowable windows for day 3 (days 3-5) and day 7 (days 6-7), unless otherwise indicated

^d Plasma ammonia should be drawn as frequently as clinically indicated, for example, every 6 hours during the first 24-hour window if the patient has a central or peripheral venous catheter.

^e Only to be drawn if dialysis is performed. Blood draws should be performed immediately upon termination of hemodialysis or hemofiltration, even if the regular time-point labs have been drawn.

^f Plasma ammonia should be drawn as frequently as clinically indicated, for example, after 48 hours, follow-up ammonia should be obtained if the prior measurement was ≥ 50 μ mol/L

^g Amino acids should be drawn as frequently as clinically indicated, for example, obtained only if ammonia also obtained (see f)

^h Safety Lab blood draw to be obtained on day 6-7, or if discharged <7d, within 24h prior to discharge

ⁱ EKG should be done before treatment begins and repeated once between Days 3-5 or before discharge

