8.4 Rationale for Sample Size and Statistical Power

All sample size and power estimates are based on 2-tailed testing, which assumes a type 1 error of 5% and achieving 80% power to detect an HR difference by treatment group and that there is no censoring as each episode will contribute information to one of the composite outcomes. We used the Cox Regression procedure in PASS (Hintze, J. PASS 11. NCSS, LLC. Kaysville, Utah, USA. www.ncss.com, 2011) to evaluate the composite time to event outcome of the earlier of the time to reach an ammonia level of 50 μ mol/L or time to discharge within hyperammonemic episodes (the unit of randomization and analysis). We evaluated HR estimates above 1, reflecting that the NCG group achieved the higher probability of achieving the composite event. Based on these considerations, a total sample size of N=146 episodes can detect an HR of 1.6, one of N=114 can detect an HR of 1.7, one of N=93 can detect an HR of 1.8 and one of N=78 can detect an HR of 1.9. These sample size estimates account for an inflated R-square as large as 0.05 between the time to event outcome and covariates reflecting baseline severity at the start of an episode. We used the inflated R-square to account for the modest effect of clustering of episodes within a person. Therefore, we consider the originally-targeted sample size of 144 episodes to be more than sufficient to meet the aims of the study. Based on our re-analysis of the time-to-event outcome, an HR of 1.7 is realistic and a sample size of 114 episodes is sufficient to detect that effect. Therefore, the target sample size will be 114 episodes.

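### Safety laboratory means are compared by arm without adjusting for each marker's own pre-dose value, which is collected in every episode, so precision is given away and chance baseline imbalance is left in.

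*Combined protocol and SAP*

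**What the plan says.** Section 8.1.2 names laboratory markers as one of three safety outcomes and gives the method: "The analysis of laboratory markers will compare the time specific and time averaged mean levels of each marker by study group". Section 8.3 says that levels and frequencies of laboratory results will be compared and that secondary analyses control for indicators of episode severity, such as peak ammonia. It describes clustering by patient for the efficacy models and does not repeat this for the laboratory comparison.

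The data for a better comparison are already planned. The pre-treatment list in section 5.4.1.2 has "Laboratory safety assessments: complete blood count (CBC), liver function tests (LFT), renal function test (RFT), amylase and lipase". Sections 2.2 and 3.1 also place a panel before treatment or at admission, followed by one around days 3 to 5 and a late one. For the late panel, Table 1 footnote h reads "Safety Lab blood draw to be obtained on day 6-7, or if discharged <7d, within 24h prior to discharge".

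On anaemia, section 2.2 says that "if a patient receives a blood transfusion during hospitalization this information will also be collected", and section 5.5.3 specifies type and number of units. No section says how haemoglobin measured after a transfusion enters the analysis.

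Section 2.2 also plans safety tests thirty days (up to six months) after the last dose. Table 1 has a Day 30 column but marks no safety laboratory draw in it.

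**The concern.** Starting values are likely to differ a good deal between patients. Section 7.1.1.3 lists renal dysfunction in MMA, neutropenia and pancreatitis in PA among the complications of the underlying diseases. Randomisation is by episode and stratified only by site (section 8.2), so neither diagnosis nor patient is balanced by design, and one patient may contribute several episodes to the same arm.

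In that setting a comparison of post-dose means carries the between-patient spread that a pre-dose covariate would largely remove. Peak ammonia is a weak substitute for a patient's own starting creatinine, ALT or haemoglobin, and the plan does not say that the peak must precede dosing. For the primary outcome the plan does allow adjustment for severity at episode baseline. At stake is the ability of a small trial to distinguish a modest organ effect from chance, in either direction.

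**Working it through.** **Inputs.** The documents give no SD, pre/post correlation, detectable difference or power for any laboratory marker. The only sample size is for the primary outcome, so it serves here just to fix the number of episodes.

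**The plan's figure.** Section 8.4 assumes a two-sided 5% level and 80% power, and says "one of N=114 can detect an HR of 1.7". The Schoenfeld formula gives (1.960 + 0.842)² / (0.25 × (ln 1.7)²) = 7.849 / 0.0704 = 111.5, so 112 events. Dividing by 1 − 0.05 for the stated R-square gives 117.4, so 118. With 114 episodes and that R-square, power is 78.9%. This is close enough to take 114 episodes, or 57 per arm under the balanced allocation of section 10.3.4.

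**Precision.** Take the marker's SD as 1 and its pre/post correlation as r (assumed). The variance of the difference in post-dose means is 2/n without adjustment and 2(1 − r²)/n with it. The difference detectable at 80% power is 2.802 × √(2/57) × √(1 − r²) = 0.525 × √(1 − r²). Episodes are treated as independent and all draws as complete.

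| Assumed r | Variance factor 1 − r² | Cut in variance | Cut in SE | Detectable difference (SD) | Power for a true 0.4 SD shift |
|---|---|---|---|---|---|
| no adjustment | 1.00 | – | – | 0.52 | 57% |
| 0.3 | 0.91 | 9% | 5% | 0.50 | 61% |
| 0.5 | 0.75 | 25% | 13% | 0.45 | 69% |
| 0.7 | 0.51 | 49% | 29% | 0.37 | 85% |
| 0.8 | 0.36 | 64% | 40% | 0.31 | 95% |

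**Chance imbalance.** The SE of the pre-dose difference is √(2/57) = 0.187 SD. An imbalance above 0.25 SD in either direction therefore has probability 18%. At r = 0.7, 0.7 × 0.25 = 0.175 SD of it passes into the unadjusted post-dose comparison.

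**Time average.** The plan does not say whether the pre-dose draw is included. If it were one of three draws, a 0.4 SD effect would shrink to 0.4 × 2/3 = 0.27 SD, with power of 41% at r = 0.5 and 36% at r = 0.7. Averaging only the two post-dose draws gives 69% and 64%. Adding pre-dose adjustment to that average gives 86% and 95%.

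**Late draw.** If a day 6-7 mean were restricted to patients still in hospital, and 60%, 40% or 25% remained, the unadjusted detectable difference would rise from 0.52 to 0.68, 0.83 or 1.05 SD. Selection could also distort it. Assume a marker-severity correlation of 0.5, with sicker patients staying: 50% of placebo and 35% or 25% of NCG episodes. A true excess of 0.40 SD then appears as 0.53 or 0.64 SD.

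**Haemoglobin.** Assume transfused shares of 2-37% on placebo and 9-63% on NCG, and a gain of 2 g/dL per transfused episode. If post-transfusion values entered the mean unchanged, a true difference of −1.0 g/dL would be observed as −0.86 to −0.48 g/dL.

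**The case against.** The case on the other side has real force. Randomisation at every episode keeps the unadjusted comparison unbiased on average, and its standard error already allows for chance imbalance. Section 8.3 does plan an adjustment, for severity. Means at each time point may include the pre-dose one, where an imbalance would be visible. The primary safety outcome is the rate of serious adverse events, not laboratory means. All of this stands, and it limits the point to lost efficiency in a secondary analysis.

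Three stronger readings are tempting, and the documents do not support them.

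- A reader might infer that late means cover only patients still in hospital. Section 3.1 and footnote h give early-discharge patients a final draw. What is missing is a rule for using it.
- A reader might infer that the pre-dose draw dilutes the time average, or that haemoglobin is counted after transfusion. Both are inferences from silence.
- A reader might infer that organ toxicity or anaemia will be missed. Adverse events are classified by CTCAE (section 7.1.1.1) and tabulated by organ system (section 8.1.2), and transfusions are recorded specifically to follow anaemia. Selection by discharge can inflate a signal as well as hide one.

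The gain should also not be turned into an effective sample size. Reading r = 0.7 as 114 / 0.51 ≈ 224 episodes would assume independent episodes, complete draws and no existing adjustment, whereas 114 episodes in 36 patients is about 3.2 each. The anaemia after hydration described in section 2.2 could also lower the pre/post correlation for haemoglobin.

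**Conclusion.** The point holds as a loss of precision. The stated laboratory analysis leaves out the most useful covariate available, the marker's own pre-dose value. Using it would cut the variance by 25% to 64% for assumed correlations of 0.5 to 0.8, and by only 9% at 0.3. These figures ignore clustering and whatever the severity adjustment already removes, so they illustrate the gain and do not predict it. There is no systematic bias from the omission, only exposure to chance imbalance.

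Three related matters are unspecified rather than wrong: whether pre-dose values enter the time average, where the pre-discharge draw sits on the time scale, and how haemoglobin after transfusion is treated. Section 2.2 and Table 1 disagree on the 30-day laboratory draw. The change is worth making before the analysis, but it concerns a secondary aim.

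**What to change.** For each marker, specify a regression of the post-dose value on the same marker's pre-dose value and arm, on the log scale if skewed, with standard errors clustered by patient. Fit it to the day 3-5 draw and, separately, to the day 6-7 or pre-discharge draw. Keep pre-dose values out of any time average.

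Use the footnote h draw for patients discharged before day 7, so that the late comparison is not confined to those still in hospital. State that its timing may differ by arm if NCG shortens the stay; the day 3-5 comparison is reported beside it for that reason.

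For haemoglobin, tabulate transfused episodes by arm next to the comparison and add a sensitivity analysis for post-transfusion values. Substituting the last value before transfusion would not be safe as the main rule. For a patient transfused before the day 3-5 draw, the last scheduled value is the pre-dose value itself, which would record no fall.

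Reconcile section 2.2 with Table 1 on the 30-day laboratory draw.

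The cost is mainly analysis-plan wording, since the panels and the transfusion log are already planned. One item needs checking: section 5.5.3 lists transfusion type and units but no clock time, and the log is completed daily. Ordering a draw and a transfusion on the same day may need a further data item.
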